RR	.7	21	31	36	41	51	63
	.65	27	40	48	54	65	77
	.6	34	51	60	67	77	88
	.5	52	72	81	86	93	98

Assuming nine shelters participating for two seasons each (18 shelter-seasons), we would have an estimated 86 percent power to detect a risk ratio of 0.50 at a 0.05 two-sided significance

level, and assuming 200 participants per shelter. The incidence during intervention periods will be compared to the incidence during non-intervention periods using general estimating equation models to control for clustering, differences in shelters, and time period. Power calculation details can be found in **Additional File 2**.

Individual enrollment criteria

Participants must fulfill all of the following inclusion criteria:

- Resident for 1 or more days at a participating shelter
- 3 months or older
- Acute cough or ≥ 2 ARI symptoms (see **Table 1** for list)
- Willing to take study medication
- Willing to comply with all study procedures, including weekly surveillance and repeat nasal swab at day 2/3 and day 5/6/7 post-treatment.
- Able to provide written, informed consent and/or assent

Table 1 – ARI trigger symptoms (participants should have ≥ 2 or more of the following new symptoms for eligibility within the past 7 days during the control period and within the past 48 hours during the intervention period)

Feeling feverish	Runny or stuffy nose
Headaches	Increased trouble with breathing
Cough	Fatigue (tiredness)
Sore throat or itchy/scratchy throat	Muscle or body aches
Nausea or vomiting	Diarrhea**
Rash**	Ear pain or ear discharge**

** *Only if under 18*

Exclusion criteria

Individuals meeting any of the following criteria will be excluded:

- Any serious or uncontrolled medical disorder or active infection that, in the opinion of the investigator, may increase the risk associated with study participation or study drug administration

- Inability to consent and/or comply with study protocol
- Individuals who have received oseltamivir or baloxavir within past 7 days for treatment of influenza
- Individuals with known hypersensitivity to baloxavir marboxil or oseltamivir
- Individuals with chronic kidney disease (CKD)

Withdrawal criteria

All participants are free to withdraw from the study at any time. Additionally, it is within the rights of the PI to withdraw any participant at any time during the study at her discretion.

Additional consent concerns

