Individuals will be recruited from staffed kiosks at each homeless shelter. Study staff will screen individuals staying at the shelter to ensure eligibility based on inclusion and exclusion criteria. Study staff will obtain informed consent from the individual or legal guardian after a full explanation has been given, an informational leaflet offered, and time allowed for consideration and questions. Once the intervention has been introduced to a shelter through randomization, study staff will require the participant to consent to the testing and receipt of the treatment drug in addition to providing questionnaire responses and corresponding nasal swab. For individuals 12-17 years of age, their legal guardian will be required to consent on their behalf prior to participation, and study staff will obtain assent from the individual.

Pre-intervention period

During the pre-intervention period, kiosks will screen and enroll individuals for the Seattle Flu Study (*see SFS Protocol*). Kiosks will be staffed at regular times 6 days a week at each shelter. Individuals aged with acute cough or ≥ 2 ARI symptoms will be eligible for participation once every two weeks. Eligible individuals who choose to participate will have a nasal swab collected and answer demographic and clinical questions on an electronic tablet. Study staff will either read the questionnaire aloud to the participant or have them complete it themselves on a tablet. The nasal swab will be transported to and tested at University of Washington. No treatment will be offered in the shelters during the pre-intervention period. All participants will receive a \$5 gift card for providing questionnaire responses and a nasal swab sample. For those that provide consent, an ROI of swabbing results will be released to their shelters' on-site providers (when applicable) for follow-up purposes.

Environmental samples (air and surface) will be collected at all shelter sites by study staff starting in the pre-intervention period and continuing through the end of the flu season. They will be tested for respiratory pathogens. Swabbing locations, schedule, and additional details can be found in the *SFS Air Filtration Environmental Sampling Protocol* and *Environmental Surface Sampling Protocol*.

Intervention period

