1. **Check eligibility:** Inclusion criteria specific to the intervention period that must be met prior to performing molecular testing include (1) ARI symptom onset within the past 48 hours and (2) not having already taken an antiviral for their current symptoms. Those

with acute cough or ≥ 2 ARI symptoms with onset between 3 and 7 days prior to enrollment are not eligible for molecular testing and antiviral treatment, but they should still complete the questionnaire and provide a nasal swab according to pre-intervention protocol. Additional inclusion and exclusion criteria can be found in section IV.

2. **Consent:** If the participant has had symptom onset within the past 48 hours, they must consent to the testing, antiviral dosage, and requisite follow-up procedures at this time. See *SFS Protocol* for additional details pertaining to non-intervention consent process.
3. **Questionnaire:** All participants must complete a REDCap survey that will ask questions gathering demographic, clinical and health behavior questions, and questions about prescription medications. This should take between 10-15 minutes to complete. After the participant has consented, the study staff member conducting the enrollment should ask whether they would prefer to complete the questionnaire themselves on the tablet or have them read the questions out loud to them and record their responses. Shelter clients may not be capable of completing the questionnaire alone if they do not have the appropriate corrective aids (glasses, contacts) for poor vision; are unfamiliar/uncomfortable with the technology and app; or have low English-language reading level. Kiosk staff should let the participant know that any question they are not comfortable providing information for they may skip and respond “Prefer not to say” in the app instead. Translated versions of the questionnaire will be available in Spanish, Tigrinya, and Amharic. We will submit translated consent forms prior to enrolling non-English speaking subjects. Telephonic translation services will also be available for participants who are not fully literate in English or their native language.
4. **Nasal swab:** One nasal swab will be collected from each participant. This singular nasal swab will both be tested on-site using the Abbott machine and will also provide a sample to be sent to the laboratory. See *SFS Protocol* for additional details pertaining to nasal swab collection procedures.

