Our research group has been asked by PHSKC Communicable Disease Epi team to help conduct contact tracing for the shelter sites where there are positive COVID-19 cases detected. Many of the shelter sites have de-congested their shelter population and moved clients to additional sites prepared to more closely adhere to social distancing efforts in a facility-setting (see Figure 3). We have modified REDCap projects so that participant enrollments may be conducted at these new shelter sites that may be housing individuals that were previously clients at shelters participating in our intervention study. These enrollments will take place as part of contact tracing efforts if a positive COVID-19 case is identified that may have been exposed to these populations, rather than having ongoing 3x/week enrollments conducted.

We will also be allowing shelter management staff to enroll in the standard surveillance component of this study from April 1 and onward for COVID-19 surveillance purposes and will be making the necessary REDCap changes to capture their sociodemographic and clinical information. Shelter staff will not be eligible for the on-site flu intervention.

Asymptomatic enrollments:

Beginning April 1, 2020 and continuing throughout the remaining study period, participation criteria for the study will be opened to any and all asymptomatic or paucisymptomatic individuals, resident or staff members, at one of the nine shelters any time there is a Research Assistant on site (see Figure 3). During both standard surveillance (pre-intervention) and intervention periods at the participants’ respective shelter, nasal swab collection will be completed with a corresponding questionnaire being conducted.

Asymptomatic/paucisymptomatic participants will receive a \$5 gift card for providing a nasal swab. Return of results to asymptomatic /paucisymptomatic participants will be conducted in the same manner as for symptomatic study participants (with the exception of on-site rapid influenza test eligibility). They will not be able to access the results of their nasal swab specimen for flu or other respiratory pathogens tested for on any online platform.

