Each shelter resident will be eligible for asymptomatic/paucisymptomatic study participation not more than once per week. All participants, regardless of symptom presentation or study period, that do not test positive for flu using the on-site Abbott will receive a card thanking them for study participation and reminding them to be tested again in one week's time.

Figure 3. All shelter sites where routine surveillance sample collection occurred, 1 October 2019 – 31 May 2021

Shelter	Max. capacity	Resident sex	Resident age range	Sleeping arrangements available
A	60	Female	≥ 18 years	Communal bunk beds
B	100	Mixed	≥ 18 years	Communal bunk beds
C	45	Mixed	18 - 25 years	Communal floor mats and bunks beds
D	185	Mixed	All ages (family shelter)	Private rooms / shared rooms / communal floor mats
E	70	Mixed	All ages (family shelter)	Private rooms / shared rooms / communal floor mats
F	60	Male	≥ 18 years	Communal bunk beds
G	275	Mixed	≥ 18 years	Private rooms / shared rooms
H	275	Mixed	All ages (family shelter)	Private rooms / shared rooms
I	45	Male	≥ 50 years	5 person dorms
J	34	Male	≥ 18 years	Individual open cubicles
K	75	Mixed	≥ 18 years	Individual open cubicles
L	200	Mixed	≥ 18 years	Communal bunk beds

M	212	Male	≥ 50 years	Communal floor mats
N	Unknown	Mixed	All ages (family shelter)	Private rooms / shared rooms
O	100	Mixed	All ages (family shelter)	Private rooms / shared rooms / communal floor mats

IV. VI. Laboratory Procedures

Molecular flu test: *(for full instructions pertaining to the use of the Abbott test instrument, see the “SFS: On-site Molecular Testing Protocol”)*

- a. There should be one Abbott machine at each shelter site that should not be moved from its address at the end of the day by the study team. The machine will be kept on-site throughout the duration of that shelter’s allocated intervention period and stored in a secure and locked location by site management staff in either the shelter clinic or administrative office. An instrument quality control test will be conducted every time the machine is moved, a new staff member is running the machine and for every new lot of cartridges
 - 1. Staff members should ensure that all required materials to run the test are available prior to enrolling patients. While the participant is working through the questionnaire, the staff member should prep the working station and VTM tube with barcode.
- b. Collect nasal swab samples according to standard protocol.

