As the genome of influenza viruses (and other respiratory viruses) can change even within a season, it is critical to archive samples for testing with the latest primers to account for this drift. Samples from this study will be held in a freezer at the University of Washington for this purpose. Aliquots from consenting participants, will be held in freezers at the University of Washington for potential other, new influenza assays that may be used in the main clinical trial, if they prove to be less expensive, easier to do and are accurate. We will amend this application if such an opportunity presents itself. Otherwise within 1 year of completing this protocol, remaining aliquots will be destroyed.

We do not currently expect to share specimens with outside investigators, but if compelling opportunities arise that will advance the overall objectives of this research, the Executive Committee (See IX. Data Safety and Monitoring section) of the study will consider such requests. They alone have the authority to make such decisions.

All biospecimens (nasal swabs) will be coded and identifiable through the study's main database. Any specimens shared with external investigators (if deemed appropriate by the Executive Committee) will have identifiers removed prior to sharing.

IX. Definitions

Influenza Like Illness in Adults (ILI): We will use the CDC definition of ILI that requires reported or measured fever ($>38^{\circ}\text{C}$) plus either cough or sore throat on one or more days preceding enrollment.

Influenza Like Illness in Infants: We will use a modified CDC definition of ILI for any infants (children less than 5 years of age), including reported or measured fever ($>38^{\circ}\text{C}$) plus cough, or runny nose, or draining ear, or nasal congestion occurring on one or more days preceding enrollment.

Episodes of influenza-like illness must be separated by 14 or more days, with day zero counted as the participant's last enrollment date.

Acute Respiratory Illness/Infection (ARI): We will use the CDC definition of ARI that includes disease that typically involves the airways within the nose and throat and may or may not include fever. ARI is generally defined by the presence of two or more symptoms such as fever, cough, runny nose or nasal congestion, or sore throat. ARI is more sensitive (broader) definition than ILI to describe illness consistent with influenza because fever/feverishness are not required.

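### A two-week re-enrolment limit written only for the control period, combined with the 7-day onset window, leaves influenza on days 1-6 after an earlier swab uncountable in control but countable in intervention

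*Combined protocol and SAP*

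**What the plan says.** These places in the combined protocol and SAP bear on when a symptomatic resident can be swabbed again and whether the result is counted:

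- **Section V, Pre-intervention period.** Symptomatic residents "will be eligible for participation once every two weeks". No exception is made for a new illness after a negative swab. No treatment is offered in this period.
- **Section V, Intervention period, step 1 (Check eligibility).** The on-site test requires "ARI symptom onset within the past 48 hours" and no antiviral already taken for the current illness. No re-enrolment interval is given. Residents with onset 3-7 days earlier are swabbed under the pre-intervention procedures; the text does not say whether the two-week limit comes with them.
- **Section IV, Individual enrollment criteria.** Participants must be "Willing to comply with all study procedures, including weekly surveillance". The term is not defined and is not tied to a period.
- **Section IV, Table 1.** Onset must fall within 7 days in the control period and within 48 hours in the intervention period.
- **Section X, Primary Outcome Measure.** Cumulative incidence is laboratory-confirmed cases over unique residents tested. The model is a Poisson mixed model for the number of positive tests, with an exposure variable based on shelter capacity. It covers symptomatic people in Year 1 (15 November 2019 to 31 March 2020).

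**The concern.** The comparison is between control and intervention time, so a case should have the same chance of being counted in both. As written, the two-week limit belongs to control time alone. Where it meets the 7-day onset window it creates a stretch after each swab in which new influenza cannot enter the count. The intervention route for recent onset has no such stretch.

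A case missed this way leaves the numerator and changes nothing else. Shelter capacity does not move, and the barred resident has already been swabbed, so is usually already among the unique residents tested. Adjusting for calendar time does not help, because the difference follows intervention status. Fewer control cases push the risk ratio upward and hide benefit.

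The primary analysis has little precision to spare. Restricted to Year 1, it rests on nine shelter-seasons. The power table in Section IV gives, at eight shelter-seasons, 52% power for a risk ratio of 0.50 and 34% for 0.60.

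**Working it through.** The plan gives no figure of its own for this point, so there is none to reproduce.

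**Step 1: which onsets are lost.** Take an enrolment swab on day 0, new influenza onset on day d, and next eligibility on day B. The case can be counted if B − d ≤ 7. Read the two-week limit as B = 14.

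- d = 6: 14 − 6 = 8 days, outside the window. The same holds for d = 1 to 5.
- d = 7: 14 − 7 = 7 days, inside the window. The same holds for d = 8 to 14.

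So 6 of the 14 onset days (days 1-6) cannot be counted. With B = 7, the oldest onset (d = 1) is 6 days old, and none is lost. With no limit, nothing is lost from this source.

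**Step 2: how many residents are in the gap.** Inputs:

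- 492 specimens a month (Section IV, Study Population).
- 1,032 residents as the target population (same place), or 1,696 as the maximum under surveillance (Section II).
- 30.4 days in a month.

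Share of residents in the gap = specimens ÷ residents ÷ 30.4 × 6.

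- 1,032 residents: 492 ÷ 1,032 ÷ 30.4 × 6 = 0.094.
- 1,696 residents: 492 ÷ 1,696 ÷ 30.4 × 6 = 0.057.

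If influenza risk is unrelated to the earlier swab, these are also the shares s of control onsets lost, about 6-9%.

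**Step 3: effect on the risk ratio when only control cases are lost.** Observed RR = true RR ÷ (1 − s).

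- True RR 0.50: 0.50 ÷ 0.943 = 0.53; 0.50 ÷ 0.906 = 0.55.
- True RR 1.00: 1 ÷ 0.943 = 1.06; 1 ÷ 0.906 = 1.10.

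**Step 4: if the limit partly or wholly carries over.** Let f be the fraction of intervention-period onsets in the gap that are swabbed through the 48-hour route, where no interval is stated. Suppose the rest follow the pre-intervention procedures and inherit the limit. Then observed RR = true RR × [1 − (1 − f)s] ÷ (1 − s). At f = 1 this is Step 3. At f = 0 the two factors cancel and there is no bias. The documents do not give f, so Step 3 is the upper end and zero the lower.

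**The case against.** The strongest reply is that one 14-day convention may have been used throughout. The two-week limit matches the definition in Section IX ("Episodes of influenza-like illness must be separated by 14 or more days"), which names no period, and pre-intervention enrolment ran under a separate surveillance protocol that may deal with new illness inside two weeks. If one limit applied in both periods, the loss largely cancels. This stands as a possibility, but the document does not state it, and the intervention-period eligibility step omits any interval. It is also fair that the shift is small beside Year 1 imprecision, and that this version is dated March 2022, so new enrolment wording cannot recover missed cases.

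Three stronger readings are tempting and are not supported.

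- **A reader might infer that the limit makes residents untreatable within 48 hours.** The limit is written for the period in which no treatment is offered, and the 48-hour rule for the period in which no limit is stated. They combine only if the limit carries over, which the document does not say.
- **A reader might infer a direct one-week against two-week conflict from the Asymptomatic enrollments text in Section V.** Its weekly cap ("Each shelter resident will be eligible for asymptomatic/paucisymptomatic study participation not more than once per week") covers asymptomatic and paucisymptomatic people, on a pathway that opens "Beginning April 1, 2020 and continuing throughout the remaining study period", after the Year 1 symptomatic analysis closes. The card in the same section is worded for everyone not positive on site, but it is a reminder, not an eligibility rule. For Year 1 the conflict rests on the two-week limit, the inclusion criterion and the unstated interval.
- **A reader might infer that the Section IX clock, which runs from the last enrolment, stops weekly-swabbed residents from ever starting a new episode.** That rule concerns influenza-like illness, and no analysis in Section X counts such episodes.

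**Conclusion.** The point holds in limited form. The re-enrolment interval for symptomatic residents is two weeks in control and unstated for recent onset in intervention, with an undefined weekly requirement in the inclusion criteria. Followed as placed, these rules ascertain cases differently by condition: control onsets on days 1-6 after a swab cannot be counted.

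The size is modest: at most about 6-9% of control onsets, with a risk ratio of 0.50 reading about 0.53-0.55 and a null about 1.06-1.10. This assumes that "will be eligible for participation once every two weeks" means at least 14 days between enrolments, strictly enforced, with each specimen from a different person, no turnover, influenza risk unrelated to the earlier swab, and no loss in intervention periods. Turnover, lax enforcement or partial carry-over would shrink it, and a common limit would largely remove it. The direction, if the limit is control-only, is against the intervention.

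**What to change.** 1. **Reconcile the text.** Make Section IV (inclusion criteria) and Section V (Pre-intervention period; Intervention period, step 1) agree on the re-enrolment interval for each period and pathway, including whether a new illness after a negative swab is exempt. Report which rule was applied in Year 1.
2. **Count cases by one rule in both periods.** In Section X, treat a further positive within 14 days of a resident's previous influenza-positive specimen as the same case. This is needed because the model is written for positive tests, and the repeat swabs on days 2/3 and 5/6/7 occur only in the intervention period (Section VIII, Table 2).
3. **Add a sensitivity analysis** that excludes intervention-period positives with onset on days 1-6 after a previous enrolment swab, to match control ascertainment. Excluding every intervention enrolment within 14 days would over-correct, because control onsets from day 7 can still be counted on day 14.

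The cost is wording and a small data step. The downside is that a few genuine intervention-period cases are dropped, in the sensitivity analysis only.

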Shelters will be randomized to different starting months for the intervention. Kiosks will continue to be staffed at regular times 6 days a week during the intervention period at each shelter. The intervention will include on-site molecular testing for influenza with the Abbott device and baloxavir (XOFLUZA) treatment for all influenza-positive individuals 12 years of age and older who weigh >40 kg, are not pregnant or breastfeeding, and do not have active malignancy, liver disease, or are immunocompromised. Individuals who meet inclusion criteria will have a nasal swab collected. Individuals with positive results who are Baloxair-eligible will be provided with a one-time dose of baloxavir. As baloxavir is an FDA-approved drug for

influenza treatment and considered standard-of-care, there will be no placebo introduced to the control groups. The description of the antiviral from the product monograph is as follows:

XOFLUZA™ is a polymerase acidic (PA) endonuclease inhibitor indicated for the treatment of acute uncomplicated influenza in patients 12 years of age and older who have been symptomatic for no more than 48 hours.

Limitations of Use: Influenza viruses change over time, and factors such as the virus type or subtype, emergence of resistance, or changes in viral virulence could diminish the clinical benefit of antiviral drugs. Consider available information on drug susceptibility patterns for circulating influenza virus strains when deciding whether to use XOFLUZA.

All influenza-positive individuals aged 3 months to 11 years, who are pregnant or breastfeeding, and adults with active malignancy, liver disease, or who are immunocompromised (Table 3) will be provided with a 5-day supply of oseltamivir. The antiviral description from the product monograph is as follows:

Oseltamivir (also known as the marketed product TAMIFLU®), is an antiviral neuraminidase inhibitor used for the treatment and prophylaxis of infection with influenza viruses A (including pandemic H1N1) and B. Oseltamivir exerts its antiviral activity by inhibiting the activity of the viral neuraminidase enzyme found on the surface of the virus, which prevents budding from the host cell, viral replication, and infectivity.

Table 3. Pre-existing conditions that necessitate oseltamivir dosage

Immunosuppression (by medication or disease)
Cancer
Liver disease

The enrollment process for participants during the intervention period is as follows:

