- **Baloxavir marboxil (XOFLUZA)** - Index cases 12 years of age and older weighing 40kg or more will receive a one-time oral dose of baloxavir based on weight within 48 hours of symptom onset. Individuals weighing 80 kg or more will receive 80 mg of baloxavir. Individuals weighing 40-80 kg, will

receive 40 mg of baloxavir. Participants will be instructed to take the medication immediately on receipt from study staff. Since baloxavir is considered standard of care, a provider does not need to be present for its dispensing and can be completed by the kiosk study staff member conducting the participant enrollment. The study staff member will observe the participant taking the dose unless the participant refuses.

Patient Body Weight (kg)	Recommended Oral Dose
40 kg to less than 80 kg	Single dose of 40 mg
At least 80 kg	Single dose of 80 mg

- **Oseltamivir (TAMIFLU)** - Index cases aged 3 months through 11 years will be provided with a 5-day supply of oseltamivir in either capsule or oral suspension form. Dosing will be determined based on weight (see table below). Children will be weighed prior to receipt of the drug in order to ensure the appropriate dosage is administered. Whether the child will be provided capsule or suspension will depend on whether they are capable of swallowing pills. Juice and crackers will be provided on-site to facilitate successful capsule administration .
 - Pregnant women, breastfeeding mothers, and adults with active malignancy, liver disease, or who are immunocompromised will receive ten 75 mg capsules to be taken twice daily for 5 days, or sufficient supply of oral suspension for 12.5 mL to be taken twice daily for 5 days.
 - The participants should be advised that the treatment can be taken with or without food, but it is less likely to cause an upset stomach if it is taken with food or milk. Participants should also be advised to continue to take oseltamivir until they finish the 5-day course, even if their symptoms begin to improve. The study staff will observe the participant taking the first dose of oseltamivir.

Weight	Treatment Dosage for 5 days	Volume of Oral Suspension (6 mg/mL) for each Dose	Number of Bottles of Oral Suspension to Dispense	Number of Capsules to Dispense (Strength)
Patients 3 months to 1 year of age				
Any weight	3mg/kg twice daily	0.5mL/kg	1 bottle	N/A
Patients 1 to 12 years of age Based on Body Weight				
15 kg or less	30 mg twice daily	5 mL	1 bottle	10 capsules (30 mg)

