15.1 kg to 23 kg	45 mg twice daily	7.5 mL	2 bottles	10 capsules (45 mg)
23.1 kg to 40 kg	60 mg twice daily	10 mL	2 bottles	20 capsules (30 mg)
40.1 kg or more	75 mg twice daily	12.5 mL	3 bottles	10 capsules (75 mg)

12. **Compensation:** All participants in both the surveillance and intervention component of this study will receive a \$5 gift card for their time (see *SFS Protocol*). Those that are eligible and enroll in the intervention component of this study will receive a \$30 gift card if tested positive and take an antiviral, with an additional \$5 gift card for each questionnaire and nasal swab that they provide during the 7-day follow-up period. The gift card ID will be logged in the REDCap application.

13. **Follow-up:**

- For any children up to age 5 who test positive for flu, we will recommend that they be seen by their pediatrician, or by an urgent care provider if they do not have a pediatrician, within 72 hours
- Research assistants will provide parents with a referral letter

- Travel vouchers will be provided for children to allow them and their caregivers to get to and from these appointments
- Following drug receipt, participants will have prospective questionnaire data and a nasal swab collected on day 2 or 3 and day 5, 6, or 7 after diagnosis. The participant will be required to return to the kiosk at their respective shelter on these days for the study staff to complete the questionnaire and provide a specimen. All participants will receive a \$30 gift card if tested positive and receive an antiviral, and an additional \$5 gift card for each subsequent nasal swab sample and symptom severity log that they provide on days 2/3 and 5/6/7, which will be logged in the REDCap application. A final follow-up questionnaire will be given on day 14 to assess for any adverse events. Any common treatment side effects experienced by the participant, which will have been shared by study staff during the consenting process, will be noted in the questionnaires during this follow up period alongside notes regarding relevant symptoms and their severity. These symptom logs will be used to monitor for the occurrence of adverse events (AEs) or serious adverse events (SAEs). See **Section XI** for additional detail about AE and SAE monitoring and reporting. (See **Appendix Additional File 2**).

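### The antiviral assignment and dosing rule contradicts itself, mainly for residents aged 12 or older who weigh 40 kg or less

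*Combined protocol and SAP*

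**What the plan says.** Section II describes the intervention as one of the two drugs for every influenza-positive case. The rule for choosing the drug appears in five places:

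| Place | Baloxavir | Oseltamivir for those aged 12 or older |
|---|---|---|
| Summary, Intervention | Age 12 or older, over 40 kg, no listed condition, not pregnant or breastfeeding | Older than 12 with immunocompromise, liver disease, pregnancy or breastfeeding (malignancy not listed) |
| IV. Study Population | Age 12 or older, no weight limit | Pregnancy, breastfeeding or a Table 3 condition, no adult limit |
| V. Intervention period | As in the Summary | Pregnancy or breastfeeding; a Table 3 condition in adults only |
| V. Obtaining antiviral, item 1 | Age 12 or older, no weight limit | As in Section IV |
| V. Obtaining antiviral, item 11 (Administer drug) | Age 12 or older, 40 kg or more | Pregnancy or breastfeeding; a Table 3 condition in adults only |

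Item 11 reads "Index cases 12 years of age and older weighing 40kg or more will receive a one-time oral dose of baloxavir", and the lowest band of its baloxavir table is "40 kg to less than 80 kg". The adult limit is in Intervention period ("adults with active malignancy, liver disease, or who are immunocompromised (Table 3) will be provided with a 5-day supply of oseltamivir") and again in item 11 ("adults with active malignancy, liver disease, or who are immunocompromised will receive ten 75 mg capsules"). The caption of Table 3 carries no age limit. The oseltamivir weight table is headed "Patients 1 to 12 years of age Based on Body Weight", with top band "40.1 kg or more".

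**The concern.** Nothing screens low-weight residents out. The inclusion and exclusion lists in Section IV and the eligibility check in Section V set a minimum age but no minimum weight. A resident who presents within 48 hours of onset consents to the antiviral before being tested, so the gap appears only once the test is positive.

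The written rule carries much of the safety burden. For baloxavir, item 11 says "a provider does not need to be present for its dispensing". Item 4 of Obtaining antiviral has kiosk staff stamp the prescriber's signature on the form at enrolment. No case-by-case prescriber review at dispensing is described, so a contradiction in the text is not clearly caught later.

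A reported outcome is also touched. Secondary outcome 2 in Section X is the proportion of on-site positives who were treated. A positive for whom the rule names no usable drug, and who gets none, would look the same there as a refusal or a missed delivery.

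**Working it through.** No design figure is involved, so the check applies each statement of the rule, read literally, to specific residents who are not pregnant or breastfeeding. B is baloxavir, O oseltamivir, and a dash means no drug. The last column is the dose that item 11 states for the drug chosen by item 1.

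| Resident | Summary | IV | V, Intervention period | V, item 1 | V, item 11 | Dose after item 1 |
|---|---|---|---|---|---|---|
| Age 15 or 30, 38 kg, no condition | - | B | - | B | - | none |
| Age 15 or 30, exactly 40 kg, no condition | - | B | - | B | B | 40 mg |
| Age 15, 38 kg, immunocompromised | O | O | - | O | - | none |
| Age 15, 45 kg, immunocompromised | O | O | - | O | B | none |
| Age 12, 45 kg, immunocompromised | - | O | - | O | B | 75 mg, if the table heading includes age 12 |
| Age 30, 45 kg, immunocompromised | O | O | O | O | O | 75 mg |

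**Under 40 kg, no condition.** Three statements exclude this resident by weight. Two assign baloxavir, for which no dose is stated, and none assigns oseltamivir. Following the text leads to one of two results:

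- No drug, contrary to Section II. In a group of n on-site positives, one such resident lowers the treated proportion by 100/n percentage points. The documents do not give n. Assuming n = 10, 20 or 50, this is 10, 5 or 2 points.
- A 40 mg baloxavir dose at a weight outside the table. The resident counts as treated, and the proportion does not change.

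**Exactly 40 kg.** The Summary and Intervention period require more than 40 kg. Item 11 and its table accept 40 kg.

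**Ages 12-17 with a Table 3 condition.** Section IV, item 1 and the Table 3 caption send them to oseltamivir. The prose of Intervention period and item 11 says adults. The weight table stops at age 12, and the flat 75 mg rule covers adults and pregnant or breastfeeding residents, so ages 13-17 have no stated dose. The size of this gap depends on weight:

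- Above 40 kg, the table's top band and the adult rule both give 75 mg twice daily: 75 - 75 = 0.
- At 23.1 to 40 kg, the table gives 60 mg and the adult rule 75 mg: 75 - 60 = 15 mg per dose.

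**Who could be affected.** Section V provides for consent and assent at ages 12-17. Figure 3 lists 15 sites, of which five (D, E, H, N, O) take all ages. Which of the 15 are the nine trial shelters is not stated, and body weights are not given. Adults under 40 kg could be at any site.

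**The case against.** The strongest reply is that a reader of the whole protocol meets less conflict than a statement-by-statement table shows. Item 1 chooses the drug and item 11 then gives the dose. On that sequence, a 15-year-old with a Table 3 condition goes to oseltamivir. A reader might infer from item 11 that such a minor should receive baloxavir, because its baloxavir sentence has no exception for these conditions. The documents do not support that: the inference needs item 11 read alone, and the Summary and Intervention period bar baloxavir for these conditions at any age. This part of the reply stands, and it reduces the second gap to a missing dose that matters mainly at 40 kg or less.

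A reader might also infer that low-weight residents probably went untreated and that the treated proportion is biased. That does not follow either. Item 1 could equally have led to a 40 mg kit, which counts as treatment. No document shows that any affected resident tested positive, and the percentage points above rest on assumed counts. The On-site Molecular Testing Protocol, which Section V names as the source of dispensing instructions, is not among these documents and may have settled the matter in practice.

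The last reply concerns timing. Version 2.8 is dated March 2022, on-site treatment was halted from April 1, 2020 for that season, and enrolment was projected to end in April 2021. Rewording cannot change a dose already given, but the reporting part of the remedy is still useful.

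None of this removes the first gap. The sequence from item 1 to item 11 still ends, below 40 kg and without a condition, in a drug with no stated dose.

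**Conclusion.** The rule is internally inconsistent. Residents aged 12 or older under 40 kg, not pregnant or breastfeeding and without a Table 3 condition, are assigned baloxavir in two places and excluded from it in three. They have no stated dose and are nowhere given oseltamivir. Followed as written, the rule gives them either no drug or baloxavir below the weight range for which a dose is stated, and the documents do not show which happened. The conflict at exactly 40 kg is a second, smaller instance of the same fault. The missing oseltamivir dose at ages 13-17 with a Table 3 condition is minor.

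The conclusion concerns the wording of the protocol. It assumes that no document outside this one set a different rule for the kiosks. The number affected is not given and is probably small. The power calculation and the primary model are unchanged, and the documents give no basis for claiming harm or a measurable shift in any outcome.

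**What to change.** Use one rule in all five places:

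- Baloxavir only for those aged 12 or older, weighing 40 kg or more, not pregnant or breastfeeding, and with no Table 3 condition. The 40 kg threshold matches item 11's dose table and settles the conflict at exactly 40 kg. Write the exceptions into item 11's baloxavir sentence.
- Oseltamivir for every other eligible positive. For assignment by condition, replace adults with participants aged 12 or older in Intervention period and item 11. In the Summary, add malignancy and include age 12.
- For dosing, keep 75 mg twice daily for pregnant or breastfeeding residents and for adults with a Table 3 condition. Extend the weight table to age 17 for the other minors. Have the medical expert team confirm the dose for ages 12-17 and for adults under 40 kg.

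Excluding residents below the threshold would also be consistent, but it would need a new eligibility criterion and a narrower statement of scope in Section II.

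For reporting, state which rule the kiosks applied. Match the on-site positives recorded on the tablet to the log of dispensed drug. Beside the treated proportion in Section X, give the number of on-site positives untreated because no drug was assigned, and the number given baloxavir below 40 kg, where weight is known. Weight may be missing for some: item 11 states weighing only for children ("Children will be weighed prior to receipt of the drug in order to ensure the appropriate dosage is administered"), and Table 2 does not name weight, although it lists only broad data categories.

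The cost is wording in five places, a wider age range in one table, a dose decision by the medical expert team and one data match. No sample size or model changes.
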